9.0 Evaluation During Study

- 9.1 A history and physical exam will be performed at two month intervals for a total of 24 months of follow up after the completion of the assigned treatment (±30 days). Note the first evaluation after radiotherapy will frequently be performed approximately 4 weeks after completion of radiotherapy and then the study will continue with history and physical exam at 2 month intervals.
- 9.2 Neuropsychological testing will be performed at each follow up visit, up to two years post radiation treatment. Reasonable effort will be made to complete this testing prior to patients meeting with their physicians and receiving information about the status of their disease.
- 9.3 Routine MR imaging of the brain performed with and without contrast will be obtained at each follow up visit at 2 month intervals (±30 days) until recurrence or up to two years post radiation treatment. Note the first evaluation after radiotherapy will frequently be performed approximately 4 weeks after completion of radiotherapy and then the study would continue with follow-up imaging at 2 month intervals. These post-treatment scans will be analyzed and compared to baseline scans for identification of regions demonstrating changes in contrast enhancement including size, heterogeneity and rim thickness. Qualitative estimation of associated T2-FLAIR changes will also be evaluated. Early stages of malignant gliomas have demonstrated decreased water diffusion. Routinely obtained diffusion weighted images and reconstructed ADC maps will be analyzed to see if there is a difference between pre- and various post-treatment scans. Based on contrast enhancing imaging features, manually selected regions of interest on ADC maps will be

quantitatively analyzed, normalized to contralateral unaffected brain parenchyma and compared on serial scans. Similarly DTI maps and cognitive functions will be correlated.

- 9.4 Medication usage (specifically steroid dose, narcotic pain medications, antiepileptic agents, psychostimulants) will be recorded. Steroid doses will be adjusted based on clinical and radiographic criteria.
- 9.5 Requirements for more frequent evaluation will be documented. Data on unscheduled follow-ups will also be documented.

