10.0 Criteria for Response and Toxicity

10.1 Definition of primary endpoint:

- 10.1.1 Time to cognitive failure on any of the 6 primary variables from the pre-specified cognitive tests (HVLT-R total recall, HVLT-R delayed recall, HVLT-R delayed recognition, TMT Part A or Part B, COWA) with failure defined as a decline that meets or exceeds the reliable change index (RCI) for each cognitive test variable. A cumulative incidence approach will be used to estimate median time to cognitive failure in order to account for the competing risks of disease progression and death. Patients experiencing disease progression or patients that died prior to experiencing cognitive failure will be considered as having had a competing event. Progressive disease frequently causes cognitive decline, and the goal of this study is to assess the impact of the radiation treatment itself on cognitive decline.
- 10.2 Definitions of secondary endpoints:
 - 10.2.1 Local control and distant control in the brain will be measured by contrast-enhanced brain MRI scan using Response Assessment in Neuro-Oncology (RANO)Criteria, as follows [50].
 - 10.2.1.1 Complete Response (CR): Requires all of the following 1) complete disappearance of all enhancing measurable and non-measurable disease sustained for a minimum of 4 weeks; 2) no new lesions; 3) stable or improving nonenhancing (T2/FLAIR) lesions; 4) patients must be off corticosteroids (or on physiologic replacement doses only); and 5) stable or improved clinically.
 - 10.2.1.2 Partial Response (PR): Requires all of the following: 1) ≥50% decrease compared with baseline in the sum of products of perpendicular diameters of all measurable enhancing lesions sustained for at least 4 weeks; 2) no progression of non-measurable disease; 3) no new lesions; 4) stable or improved non-enhancing (T2/FLAIR) lesions on the same

or lower dose of corticosteroids compared with the baseline scan; 5) stable or improved clinically.

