10.2.1.3 Progressive Disease (PD): Defined as any of the following 1) \geq 25% increase in the sum of the products of perpendicular diameters of enhancing lesions compared with the smallest tumor measurement obtained either at baseline (if no decrease) or best response, on stable or increasing dose of corticosteroids; 2) significant increase in T2/FLAIR nonenhancing lesion on stable or increasing doses of corticosteroids compared with baseline or best response not caused by comorbid events (i.e. radiation therapy. demvelination, ischemic injury postoperative changes); 3) any new lesion; 4) clear clinical deterioration not attributable to other causes apart from tumor (i.e. seizures, medication adverse effects, complications of therapy, cerebrovascular events, infection, or decrease in corticosteroid dose); 5) failure to return for evaluation due to death or deteriorating condition; 6) clear progression of non-measurable disease.

When making the diagnosis of progressive disease it is import to recognize the possibility of pseudo-progression, especially if the patient is clinically stable. In those situations, treatment should continue and status of local control should be evaluated with a repeat interval scan. If the subsequent scan confirms progression then the date of progression should be backdated to the original scan suggesting progression.

- 10.2.1.4 Stable Disease (SD): Requires all of the following 1) does not qualify for complete response, partial response, or progression; 2) stable FLAIR/T2 lesions on corticosteroid dose no greater than at baseline; 3) clinical status stable.
- 10.2.1.5 For local control, PD is considered local failure, or stable disease with deterioration of the neurological examination with a grade III or worse toxicity on the CTCAE v.4.0 scale (see Appendix). All others (CR, PR, asymptomatic SD) are deemed success.
- 10.2.2 Overall survival will be measured from registration until death. After 2 years of follow-up event monitoring will be used.
 - 10.2.2.1 Patients with unknown vital status will be censored at the date of last visit or MRI scan.
- 10.2.3 Quality of life will be measured at each two month interval follow up visit out to two years using the EORTC QLQ C30/BN20 and the MD Anderson Symptom Inventory Brain Tumor (MDASI-BT).

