- 12.3 Primary Analysis: The analysis will be performed on the intention-to-treat principle. Considering those patients who are not evaluable as treatment failures. We will use the methods of Gooley et al. [52]to estimate the cumulative incidence of cognitive failure in each treatment arm, considering progressive disease and death before cognitive failure as competing events. We will estimate the cumulative incidence of cognitive failure at 4 months with 95% confidence intervals. We will use the methods of Fine and Gray [53]to test for a difference between treatment arms with respect to the cumulative incidence of cognitive failure, considering progressive disease and death before and death before and death before cognitive failure as competing events. We will use the methods of Fine and Gray [53]to test for a difference between treatment arms with respect to the cumulative incidence of cognitive failure, considering progressive disease and death before cognitive failure as competing events. Our model will include treatment arm and the stratification factors used at randomization.
- 12.4 Secondary Analysis:

We will repeat the primary analysis on only those patients considered evaluable. All the secondary analyses described below will be performed using all patients as well as using only evaluable patients. We will estimate the cumulative incidence of local failure using the methods of Gooley et al. considering death as a competing event. We will model the time to local failure using the methods of Fine and Gray to test for differences between treatment arms, considering death as a competing event. Our model will include treatment arm and the stratification factors used at randomization, as well as selected dosimetric parameters. We will similarly analyze time to distant failure.

We will use the product limit estimator of Kaplan and Meier [54] to estimate overall survival stratified by treatment arm. We will also use Cox proportional hazards regression [55] to model overall survival as a function of treatment arm and the stratification factors used at randomization.

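### Study MRI stops at first recurrence, yet distant failure is analysed with death as the only competing event, so what its incidence estimates depends on an unstated rule

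*Combined protocol and SAP*

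**What the plan says.** Section 9.3 schedules study MRI every two months "until recurrence or up to two years post radiation treatment". Section 10.2.1 makes MRI the instrument for both endpoints: "Local control and distant control in the brain will be measured by contrast-enhanced brain MRI scan". Clinical visits are not tied to recurrence. Section 9.1 says "A history and physical exam will be performed at two month intervals for a total of 24 months of follow up", and section 9.5 adds that unscheduled follow-up is documented.

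Section 12.4 states for local failure: "We will estimate the cumulative incidence of local failure using the methods of Gooley et al. considering death as a competing event". The arm comparison uses Fine and Gray "to test for differences between treatment arms, considering death as a competing event". For distant failure it says only "We will similarly analyze time to distant failure". By contrast, section 12.3 names both progression and death as competing events for the primary endpoint.

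On definitions, section 10.2.1.5 says "For local control, PD is considered local failure", and the list of progression criteria in 10.2.1.3 includes "3) any new lesion" with no limit on site. Distant failure has no event definition of its own.

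**The concern.** After a local recurrence, the scan that would show a distant failure is no longer scheduled. A death-only competing-risk analysis still needs a rule for that patient's remaining follow-up, and the plan gives none. Three rules are possible: censor at local failure, keep at risk until death, or count local failure as a competing event. They estimate different things, and an analyst could choose among them after seeing the data.

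At stake is a secondary result reported by arm. A distant failure rate from this trial would be read as the proportion of patients who fail distantly. Under the first two rules, the reported figure could be about twice the distant-first rate, or about two thirds of the rate of distant failure at any time.

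**Working it through.** **The plan's own figures.** The documents give no rate, event count or power for local or distant failure. The 43 events in section 12.2 belong to cognitive failure and do not bear on this point. Every hazard below is an assumption, taken as constant and independent.

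**Reading A: censored at local failure.** Let L, D and M be the monthly hazards of local failure, distant failure and death without recurrence.

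- Distant-first incidence by month t: D/(L+D+M) × (1 − exp(−(L+D+M)t)).
- Estimate if local failures are censored: D/(D+M) × (1 − exp(−(D+M)t)).

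With L = 0.06, D = 0.015, M = 0.01 and t = 24:

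- Distant-first: 0.015/0.085 × (1 − exp(−2.04)) = 0.1765 × 0.8700 = 15.4%.
- Censored: 0.015/0.025 × (1 − exp(−0.60)) = 0.60 × 0.4512 = 27.1%.
- Ratio: 1.76.

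The same formulas at earlier times:

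| Month | Distant-first | Censored estimate | Ratio |
|---|---|---|---|
| 6 | 7.1% | 8.4% | 1.19 |
| 12 | 11.3% | 15.5% | 1.38 |
| 24 | 15.4% | 27.1% | 1.76 |

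At 24 months, hazards of (0.05, 0.01, 0.01) give 11.6% reading 19.1%, and (0.07, 0.02, 0.02) give 16.9% reading 30.9%.

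A wider grid of 60 scenarios took median time to progression of 5 to 14 months, a distant-first share of 5% to 50%, and death without progression of 0.002 to 0.02 per month:

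| Month | Range of ratio | Scenarios above 1.5 |
|---|---|---|
| 6 | 1.07–1.44 | 0 of 60 |
| 12 | 1.14–1.96 | 20 of 60 |
| 24 | 1.26–3.15 | 48 of 60 |

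**Reading B: kept at risk until death.** Only distant failures that come first are seen, and local-first patients remain in the denominator. The estimate then equals distant-first incidence (ratio 1.00). To compare it with distant failure at any time before death, a simulation assumed a median of 7 months to progression, death at 0.01 per month without progression and 0.09 per month after it, and an unchanged distant hazard after local recurrence. At 24 months:

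| Distant share of first failures | Estimate (distant-first) | Distant at any time | Ratio |
|---|---|---|---|
| 10% | 8.4% | 14.2% | 0.59 |
| 20% | 16.8% | 26.5% | 0.64 |
| 30% | 25.3% | 37.3% | 0.68 |
| 50% | 42.1% | 54.8% | 0.77 |

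In the 20% row, Reading A would report 34.0%. The same patients thus give 34.0% or 16.8%, against 26.5% for distant failure at any time.

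**Local failure.** Sections 10.2.1.3 and 10.2.1.5 together make a new lesion at any site a local failure. A distant-first patient therefore already has the local event and is not censored for it. In the 20% case, the total hazard is ln 2/7 + 0.01 = 0.0990 + 0.01 = 0.1090. True local-first failure at 24 months is 0.0792/0.1090 × (1 − exp(−2.616)) = 67.4%. Progression at any site is 0.0990/0.1090 × (1 − exp(−2.616)) = 84.2%, a ratio of 1.25. That excess comes from the definition, not from the choice of competing event.

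**Between arms.** Hold D = 0.015 and M = 0.01 in both arms, and let L be 0.06 in one and 0.03 in the other. The censored estimate at 24 months is 27.1% in both. Distant-first incidence is 15.4% against 0.015/0.055 × (1 − exp(−1.32)) = 20.0%.

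**The case against.** A reader might infer that both incidences are overstated, and distant failure by more than half. The documents do not support that, for four reasons.

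- **Censoring is not stated.** The only written censoring rule (10.2.2.1) concerns unknown vital status for overall survival. Visits run to 24 months and deaths are monitored afterwards, so keeping a patient at risk until death is feasible. The contrast with section 12.3 makes censoring a plausible reading, but it remains an inference. This objection stands: the direction of any error depends on the rule.
- **The size is not in the documents.** It rests on assumed hazards and on the 24-month time point, and section 12.4 names no time point. This stands too.
- **Censoring cannot inflate local failure as that event is defined,** because a new distant lesion already counts as one. This stands and exposes a separate defect.
- **Unequal local failure need not distort the censored comparison.** With independent hazards the censored estimate is the same in both arms, while the first-failure estimate shifts. A distortion argument would need dependence between the two failure types, for which the documents give no figures.

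It can also be said that visits and unscheduled follow-up may still reveal distant failures, and that this is an unpowered secondary analysis in a phase II screening trial. Both are fair and limit the weight of the point. But occasional detection is not scheduled imaging, and none of these objections supplies the missing rule or the missing definition.

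**Conclusion.** The point holds as a mismatch between the imaging schedule and the distant-failure analysis, not as a demonstrated bias in one direction. If patients are censored at local failure, the estimate is too high for distant-first failure: 15% reads 27% at 24 months under the assumed hazards, with ratios of 1.19 at 6 months and 1.38 at 12. If they are kept at risk until death, it is correct for distant-first failure and too low for distant failure at any time, with ratios of 0.59 to 0.77 at 24 months under the simulated rates. Under neither rule does it estimate distant failure at any time, which is how the endpoint reads as named. In addition, local and distant failure are not separate events as written. The primary endpoint is unaffected. This merits a correction before the analysis, in proportion to a secondary endpoint.

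**What to change.** 1. In section 10.2.1, define distant failure as an event of its own and reconcile 10.2.1.5 with it, so that a new lesion outside the local region is not also a local failure.
2. Record the site of first progression from the scan that dates it.
3. In section 12.4, analyse site of first failure. For distant failure, treat local-first failure and death as competing events. Once the definitions are separate, treat distant-first failure and death as competing events for local failure. State how simultaneous failure at both sites is classified.
4. Report the two incidences together by arm.

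The cost is a few sentences in sections 10.2.1 and 12.4 and one data field. There are two downsides. The result is first failure at a site, not failure ever; the latter would need imaging after recurrence, which section 9.3 does not schedule. And a difference between arms in local failure will shift distant-first incidence even if the distant hazard is equal (15.4% against 20.0% in the example above), which is why the two must be read side by side.

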Decreased dosage to critical normal brain tissues has been suggested to translate into improved cognitive function. Merchant et al. compared dose characteristics for four types of common childhood brain tumors treated using conformal protons versus photons and in dosevolume modeling systems found that proton plans resulted in better cognitive outcomes. Specific advantages included decreased IQ loss, less cochlea damage, and decreased endocrine effects[10]. The study of long term benefit of proton therapy in pediatric patients will require years of follow up but the preliminary results are encouraging. Similarly Arvold et al. modeled doses for protons versus photons in the treatment of benign meningiomas. They showed that protons could decrease the risk of radiation associated secondary malignancies by half and that lower doses to critical structures supporting cognitive functions such as memory including the temporal lobe and hippocampus could be achieved with proton plans [21].

While the theoretical dosimetric advantages of proton plans are intriguing we do not have randomized data comparing cognitive outcomes in glioblastoma patients treated with these two modalities. We hypothesize that IMPT will result in improved cognitive outcomes. In this trial we propose to address this question by prospectively randomizing patients with glioblastoma to treatment with IMRT versus IMPT. Patients will be stratified by RPA class, Mini Mental Status Examination score (21-26 vs. 27-30)[17], and age (less than 65 vs. 65 and older). These factors are known to have prognostic significance. The primary endpoint will be time to first cognitive failure on any of the following six cognitive test variables: HVLT-R Total Recall, HVLT-R Delayed Recall, HVLT-R Delayed Recognition, COWA, and TMT A or B. Secondary endpoints will include local control and overall survival outcomes as well as quality of life. Addressing this question in a prospective randomized fashion can be accomplished at MDACC given the high volume of cancer patients with glioblastoma treated at our center.

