7.0 Treatment Plan

- 7.1 Eligible patients will be randomized in equal numbers to each treatment arm using CORe. Randomization will be stratified using the following factors:7.1.1 RPA class (III or IV vs. V)
 - 7.1.2 Mini Mental Status Examination score (21-26 vs. 27-30)
 - 7.1.3 Age (less than 65 vs. 65 or older)
- 7.2 Following randomization, insurance pre-authorization will be obtained for the specified treatment modality. If a patient's insurance will not cover payment for the assigned treatment arm, that patient will be removed from the study and will be treated off protocol.
- 7.3 Radiation target definition for glioblastoma as follows. GTV defined as tumor cavity and any T1 tumor enhancement. CTV will include GTV + 2 cm margin customized to include FLAIR enhancement (if thought by the radiation oncologist to be tumor) and exclude bone, fascia, and other anatomical barriers. PTV-50 will include CTV + 3-5 mm and will be treated to 50 Gy in 30 fractions. PTV-60 boost volume will include GTV + 3-5 mm and will be treated to 60 Gy in 30 fractions.
- 7.4 For patients randomized to IMRT, treatment will be planned using Pinnacle software system. Planning will be based on non contrast CT images obtained at time of simulation in addition to MRI scan. Treatment will be delivered using linear accelerator. Fractionated radiation will be delivered daily M-F with weekends off for all patients. IMRT plans use a configuration of five to seven isocentric 6-MV photon beams delivered in a step-and-shoot technique. For inverse planning specified dose constraints are given to organs at risk including the brainstem, spinal cord, optic chiasm, optic nerves, and cochlea.

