12.0 Statistical Considerations

- 12.1 Randomization procedure: A stratified block randomization procedure will be used. Randomization will be performed using CORe. The randomization strata are as defined above in section 7.0, and the block size will be 6. Patients who withdraw from the study after randomization, but prior to receiving treatment will be considered a cancel and replaced.
- 12.2 Sample size: With IMRT the cognitive function failure rate at 4 months is 45%, based off of comparative analyses of the cognitive failure rate of RTOG 0614 and compared to the cognitive impairment seen on RTOG 0525; we hope to demonstrate that IMPT can achieve a cognitive function failure rate at 4 months of only 30%. We assume the time to cognitive failure in each treatment arm follows an exponential distribution. A cognitive failure rate of 45% at 4 months then implies a median time to cognitive failure of 4.6 months, while a cognitive failure rate of 30% at 4 months implies a median time to cognitive failure to cognitive failure of 7.8 months.

We will use a 1-sided significance level of 0.20 as suggested by Rubinstein et al. [51]for phase II screening trials. We expect to enroll 2 patients per month, and we will randomize 60 evaluable patients (30 to each treatment arm). We will have 80% power to detect an improvement in cognitive failure at 4 months from 45% in the IMRT arm to 30% in the IMPT arm. We expect to observe 43 events, and the analysis will be performed once we have observed these events. We define evaluable patients as those who have received the assigned treatment *and* completed baseline and at least one follow-up neurocognitive testing. We expect we will need an over accrual of 33% to account for those patients not evaluable. Therefore the target total enrollment sample size is 90 patients to accrue a total of 60 evaluable patients. We expect to observe 43 events, and we expect the trial to take 41 months to observe these events.

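### The overall survival Cox model adjusts for age and RPA class only as two-level randomisation strata; adding age in years and three-level RPA would use prognostic information already in hand

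*Combined protocol and SAP*

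**What the plan says.** Section 12.4 estimates overall survival by Kaplan-Meier and uses Cox regression "to model overall survival as a function of treatment arm and the stratification factors used at randomization". Section 12.1 refers to section 7.0 for the strata. There, 7.1.1 gives "RPA class (III or IV vs. V"), 7.1.3 gives "Age (less than 65 vs. 65 or older"), and 7.1.2 splits the Mini Mental Status Examination (MMSE) score at 21-26 versus 27-30. Section 12 states no other coding, and no arm-comparison model lists age in years or three-level RPA.

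Section 4.0 says of the three factors: "These factors are known to have prognostic significance". It gives no effect sizes and does not name the outcome.

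Three-level RPA has to exist. Eligibility (6.1) admits classes III, IV and V, and the molecular-clinical classifier (5.2.4, analysed in 12.4) is built from all three. The documents do not say that exact age is recorded, but this is a safe inference from the age criterion (6.2), the 65-year stratum and the age-based test norms in 8.2.

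**The concern.** Bands are needed to randomise, but an adjusted model is not confined to them. Stratified blocks balance the arms on the bands. They do not balance a 30-year-old against a 64-year-old, or class III against class IV. If risk varies within bands, a strata-only Cox model leaves chance imbalance there uncorrected. Because omitted prognostic variation also pulls a hazard ratio towards 1, it gives up some power as well. Survival is a secondary endpoint in a trial of 90 patients, so even a modest gain at no data cost is worth having.

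**Working it through.** **1. The plan's own figure.** Section 12.2 assumes exponential times and 45% versus 30% cognitive failure at 4 months, and sets the test level: "We will use a 1-sided significance level of 0.20".
- HR = ln(0.70)/ln(0.55) = 0.597, so ln HR = -0.516.
- Schoenfeld events = 4 × (0.842 + 0.842)² / 0.516² = 42.5, rounded up to 43. Power at 43 events is 80.3%.

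The stated 43 events and 80% power reproduce. The formula contains no covariates, so the coding of age and RPA does not touch them.

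**2. What the age cut retains.** For a normal variable cut at standardised point c, with a proportion p above it, the squared correlation with the indicator is φ(c)²/[p(1-p)]. Age mean and SD are assumptions.
- Mean 55, SD 11: c = 0.909, φ = 0.264, p = 0.182, giving 0.47.
- Mean 60, SD 12: c = 0.417, φ = 0.366, p = 0.338, giving 0.60.

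The band keeps roughly 47% to 60% of the linear information in age.

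**3. A plausible number of deaths.** Section 4.0 cites 27.2% two-year survival, so the hazard is -ln(0.272)/24 = 0.0542 per month. Assume 45 months of accrual (90 patients at 2 per month), analysis 18 months after the last entry, and HR 0.6.
- Proportion dead, control: 1 - (e^-0.976 - e^-3.415)/2.439 = 0.859.
- Proportion dead, experimental (hazard 0.0325): 1 - (e^-0.585 - e^-2.049)/1.463 = 0.707.
- Deaths: 45 × (0.859 + 0.707) ≈ 70.

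**4. Survival power by simulation.** Assumptions: 90 patients, 70 deaths, stratified blocks of 6; age mean 58, SD 12; RPA III/IV/V in 20/55/25%, independent of age; MMSE 21-26 in 30% with log HR 0.3. Log HR per decade of age and per RPA step: weak 0.15 and 0.2, moderate 0.3 and 0.4, strong 0.5 and 0.6. There were 4,000 trials per setting (Monte Carlo SE about 0.8 points or less). With log-linear effects, *replacing* the bands by the full values gave:

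| Effects | One-sided 0.20, HR 0.70: bands → full | One-sided 0.025, HR 0.60: bands → full |
|---|---|---|
| Weak | 73.6% → 73.7% | 55.1% → 57.0% |
| Moderate | 69.5% → 72.3% | 51.3% → 55.3% |
| Strong | 67.3% → 72.7% | 47.2% → 56.2% |

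Simulated type I error was 0.206-0.214 (bands) and 0.206-0.223 (full) at nominal 0.20, and 0.028-0.034 and 0.026-0.029 at nominal 0.025.

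**5. Adding instead of replacing.** If the true effects are steps at the protocol's own cuts, replacement can lose up to about 5 points for survival. *Adding* the full values beside the strata guards against this. In a separate run with log-linear effects the gain was about 0 points (weak), 2-3 (moderate) and 3-7 (strong), for example 48.0% to 54.8% with strong effects at one-sided 0.025. With step effects the cost was at most about 1 point. Type I error changed little.

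**6. The primary-type test, for comparison.** Settings: 60 patients, 43 events, HR 0.597, one-sided 0.20. Cox stands in for Fine-Gray, with no competing events. Bands versus full replacement, log-linear: 79.5% vs 78.9% (no effect), 77.6% vs 77.7% (weak), 76.6% vs 78.5% (moderate), 73.7% vs 77.8% (strong). With step effects, in another run: 78.7% vs 78.1% (weak) and 82.2% vs 80.2% (moderate). The change is small and its sign depends on the assumed shape.

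**The case against.** The strongest reply is that nothing is wrong. Adjusting for the factors as randomised is pre-specified, valid and matched to the design, and it controls type I error. That stands: this is a choice about efficiency.

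Second, no gain can be sized from the documents. They give no effect sizes or shape for age and RPA, and no alpha, power or target effect for survival. The only stated level, one-sided 0.20, belongs to cognitive failure. This also stands, and is why the size is given as a range. The shape argument defeats replacing the strata, but has little force against adding to them.

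Third, the same reasoning covers MMSE, which is banded too. That is true. This point sizes only age and RPA, and leaves MMSE as its stratum.

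A reader might infer more than the documents support:
- *That the primary model in 12.3 should be rewritten.* Its endpoint is cognitive failure with progression and death as competing events. Section 4.0 does not say for which outcome the factors are prognostic, the simulated change runs from about +4 to -2 points, and neither simulation includes competing events.
- *That the stated power is overstated.* The calculation has no covariates and reproduces.
- *That exact age is stated to be recorded.* It is inferred.

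**Conclusion.** The point holds as an optional improvement to one secondary model. As written, the survival Cox model uses two levels each of age and RPA and leaves within-band information unused. Under the assumptions in the working, adding the finer values offers a power gain ranging from nothing to about 7 points, against a loss of at most about 1 point. The upper end needs strong, log-linear effects. None of these effect sizes comes from the documents. It is a minor point: no stated figure changes, and the planned analysis remains valid if the sponsor keeps it.

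**What to change.** In 12.4, state that the overall survival Cox model includes treatment arm, the three stratification factors, age in years (linear) and RPA class in three levels (III, IV, V). Report the strata-only model as a sensitivity analysis. Since the two-level RPA stratum is nested in the three-level class, the additions amount to one term for age and one for class III versus IV.

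Leave the 12.3 primary model and the randomisation strata unchanged. A full-value version of the primary model may be pre-specified as a sensitivity analysis.

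Cost: one sentence, fixed before the analysis, and two extra degrees of freedom. No new data are needed, provided the sponsor confirms that exact age is in the database. The reported hazard ratio would then be conditional on the larger covariate set, which the report should say.
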